Colonic Propionate, Appetite, and Weight Loss (ProAp)

NCT03322514

Date: 24/01/2017

Protocol:**1. INTRODUCTION****DIET AND OBESITY:**

Obesity has reached epidemic proportions worldwide. In the United Kingdom, 58% of adult women and 65% of adult men are either overweight or obese (Health and Social Care Information Centre 2014), with the expectation that rates will increase (Ng et al. 2014). Obesity, mainly caused by a chronic positive energy balance, is a known risk factor that contributes to the development of type 2 diabetes and cardiovascular diseases, and the subsequent morbidities and mortalities (Kopelman 2007). A positive energy balance is inevitable with the composition of current western diet that contain refined (fibre-depleted) carbohydrates that are consumed quickly, and have minimal effects on long-term satiety (Cleave 1974; Heaton 1973).

NONDIGESTIBLE CARBOHYDRATES:

The quality and quantity of diet has changed dramatically over the last fifty years. Of which, carbohydrates have the most significant changes; from unprocessed fruits and vegetables based carbohydrates to more processed cereal based ones (Cordain et al. 2005). Epidemiological studies have shown that, as a result, ancestral diets had greater amounts of Non-Digestible Carbohydrates (NDC) than modern diets (>100g/day compared to <15g/day) with the inclusion of more indigestible intact cell wall plant material, such as tubers, grasses and sedges (Eaton 2006). A strong association has been established between increased weight gain with decreased NDC intake (Liu et al. 2003). Furthermore, increasing intake of NDC have shown to induce satiety and improve body composition in animals (So et al. 2007) and humans (Bouché et al. 2002).

LOW CALORIC HIGH NDC DIET IN LOSING WEIGHT

Applying energy-restricted diets is one of the first steps to treat obesity. However, weight regain in weight maintenance period could happen due to resting energy expenditure reduction and lean mass loss. The inclusion of specific foods to the nutritional intervention is being investigated in order to produce persistent weight losses (Abete et al. 2008). It was suggested earlier that the addition of high fibre NDC foods to a hypocaloric diet would help reducing the incidence of metabolic syndrome and increasing the dietary compliance (Hermana et al, 2011). The high fibre content in combination with a low glycemic index diet, can both result in higher satiety effects with an increased mitochondrial oxidation, all favour weight loss.

PROPIONATE AND THE FFAR2 RECEPTOR:

Production of short chain fatty acids (SCFA) is the main by-product of NDC colonic fermentation (Pawlak et al. 2004). Of them, colonic propionate was found to play a critical role directly in the colon and systematically after its absorption into the circulation (Wong et al. 2006). Free Fatty Acid Receptor 2 (previously known as orphan G-coupled Protein Receptor 43) has been discovered to have high affinity to propionate (Brown et al. 2003). It is expressed on the distal ileum and colon L-enteroendocrine cells (Karaki et al. 2008), adipocytes and certain monocytes lineage (Hong et al. 2005).

THE ROLE OF PROPIONATE IN GUT HORMONE RELEASE AND APPETITE REGULATION:

The L-enteroendocrine colonic cells are responsible of secreting anorexic gut hormones (PYY and GLP-1) physiologically in response to food. These hormones are capable of inducing satiety through signalling the brain appetite centre (Murphy & Bloom 2006). Propionate-induced FFAR2 activation have found to cause the release of these hormones *in vitro*. Moreover, NDC ingestion was found to stimulate the release of these hormones in animals, resulting in decreasing food ingestion (Delzenne et al. 2005). Propionate was shown to replicate the same effects in further studies, suggesting the owning of the beneficial effects of NDC on appetite and gut hormones to propionate production.

SHORT CHAIN FATTY ACID ESTER:

Administering NDCs that promote the production of propionate is an attractive way to increase the level of propionate over an extended period of time. However, due to variability of the gut microbita activity, administering high proportions ($\geq 35\text{g/d}$) of dietary fibres in human diets to increase colonic propionate does not reliably or predictably provide the same SCFA levels in colon or systemically (Cummings 1981). Oral propionate supplementation is another method, but unfortunately its short plasma half-life, poor palatability, and the fact that its main absorption happens in the small intestine limit its use as a food supplement (Frost et al. 2003).

A novel system has been developed by [name], (Scottish Universities Environmental Research Centre (SUERC)). This molecule of inulin ($\beta(2-1)$ linked polymer of fructose) carrier with an ester linked to propionate (propionate ester) was demonstrated to reliably and reproducibly increase colonic propionate while prevent the side effects of NDC (Chambers et al. 2015). Thus, propionate is only released when the carrier molecule inulin is fermented by colon microflora, which was estimated to be 180 minutes post-ingestion. (Chambers et al. 2014). Chambers et al. (2015) were able to show that 10g of Inulin-Propionate Esters (IPE) has the ability to deliver 2.4g of propionate to the colon, that is an increment of 2.5-fold of propionate production in the colon, a level that is achieved only with 60g/d via traditional dietary fibre supplementation.

The same group has also demonstrated that while the acute administration of this supplement caused increments in Plasma GLP-1 and PYY and reduced food ingestion, the long term (24 weeks) supplementation of propionate ester significantly reduced body weight gain and the development of abdominal adipose tissue (Chambers et al. 2014). Interestingly, none of the long term participants reported any side effects from the intake of propionate esters. Increasing colonic propionate is, therefore, one of the attractive strategies to manage weight and diabetes risk factors.

The current protocol aims to investigate the impact of the propionate ester in conjugation with restricted diet on appetite and weight loss.

2. Study: Effect of increased colonic propionate on weight loss during a hypo-caloric diet.

Study methodology: A randomised, control, paralleled study.

Participants: 70 overweight and obese healthy male and female volunteers aged between 18 and 65 years with body mass index (BMI) of 25-35 kg/m².

Support of number of volunteers: Based on previous work we anticipate that a hypo-caloric diet alone will cause a weight loss of 3.0 ± 2.5 kg, whilst the addition of propionate-ester will cause a weight loss of 5.0 ± 2.5 kg. A power calculation shows that 26 volunteers will be need per group to detect a significant difference between groups ($p=0.05$, 0.80 power). 70 volunteers will be recruited to allow a 25% drop-out rate.

Visit 1: Health Screening

Participants will attend the NIHR/Wellcome Trust Imperial Clinical Research Facility at Hammersmith Hospital where their eligibility will be assessed. They will have a blood test (FBC, ALT, HbA1C, renal function, and lipids) and height and weight measurements will also be taken. They will also have an electrocardiogram (ECG) and blood pressure will be recorded. All women of childbearing age will have a pregnancy test.

Participants will be told not to start any other new diets or intensive exercise regimes during the study period as this may give us conflicting results.

Visit 2: Acclimatization visit (Week 0)

The main objective of this visit is to fully acclimatize the participants to the study before the baseline visit.

The day prior to the study visit, participants will be requested to refrain from strenuous exercise and alcohol. Participants will then be requested to fast overnight (they are allowed to drink water) and will come to the NIHR/Wellcome Trust Imperial Clinical Research Facility at Hammersmith Hospital the following morning. Fasting saline flushes will be done through an intravenous peripheral cannula at -10 and 0 min. Resting energy expenditure will be measured with a standard indirect calorimeter. The calorimeter captures expired air from a large, transparent canopy, worn over the head and thorax, and is typically very well tolerated. Each participant will be asked to lie in a semi-recumbent position under the canopy. Once the carbon dioxide content of the air entering the chamber has stabilised, measurements will be taken for 20 min in order to assess the participants' resting metabolic rate (RMR) and respiratory quotient (RQ). The calories needed per day for each subject will be estimated and a -500 kcal/day diet will be provided to the participants to follow for the rest study period. Participants will be asked to complete a 7days-food diary in order to form a suitable individualised diet. A weight management booklet will be designed to each participant, where their resting energy requirement will be estimated and a healthy diet plan will be designed. This will also include a supplementary material of the portions required and list of different substitutes to be taken per food group. The same booklet content was previously designed and used in a trial that was ethically approved with a reference number of 12/LO/0139 version 2: 31/07/2012.

Participants will then receive a standardised breakfast (0 min). Postprandial saline flushes will be given at 15, 30, 60, 90, 120, 180, and 240 min.

Appetite and satiety will be assessed by visual analogue scale every 60 min and breath hydrogen concentration will be measured at the same time, as a marker of colonic fermentation. Food intake will be assessed at 240 min by offering a free buffet meal served in excess.

Visit 3: Study visit 1 (Week 1)

The same measurements collected during the acclimatization visit will be repeated. The only difference would be in collecting 10 ml of postprandial blood, instead of flushing saline, at each time point of 15, 30, 60, 90, 120, 180, and 240 min to measure hormones and metabolites. These will include glucose, insulin, gastrointestinal and appetite hormones (GLP-1, pro-glucagon-derived peptide, PYY, PP, Ghrelin, Cholecystokinin), and short chain fatty acids level

Participants will be randomised to take 10 g of Propionate ester or Inulin (control) dietary supplement once a day for 84 days (12 weeks). Supplements will be given to participants in ready-to-use sachets and instructed to mix the contents into their -500 kcal/day individual diet. An independent researcher (i.e. not linked to the study) will be given the task of randomisation, which will be by sealed envelopes.

Urine will be collected throughout the study visit to measure propionate and urea concentrations. Subjects will empty their bladder before the test breakfast and collect all urine thereafter for a period of 240 min. Subjects will be provided with an appropriate measurement container to collect urine and will be asked to note the total volume following each collection.

Subjects will be asked to collect a stool sample to assess propionate levels. Subjects will collect a sample of the first stool they pass after 10:00 pm on the study day. Participants will be provided with detailed instructions of how to do this and will be given appropriate containers.

Visits 4 and 5: Study visits 2, 3 (Week 4 and week 8):

Will involve short visits to monitor weight and dietary compliance to the diet, through collecting 7-days food intake diary and taking anthropometry measurements.

Visit 6: Study visit 4 (Week 12):

At the end of 84 day supplementation period, participants will attend the NIHR/Wellcome Trust Imperial Clinical Research Facility at Hammersmith Hospital to and all measurements collected during Study Visit 1 will be repeated.

PARTICIPANT ENTRY**INCLUSION CRITERIA**

- Healthy overweight and obese volunteers (body mass index (BMI) of 25-35 kg/m²)
- Age between 18-65 years (inclusive)
- Having blood results for the following tests in the ranges of:
 - HbA1C 20-41 mmol/mol haemoglobin
 - ALT 0-40 IU/L
 - FBC :

| TEST | MALE | FEMALE |
|---------------------------------|-------------|-------------|
| WBC (x10 ⁹ /L) | 4.2-10.6 | 4.2-11.2 |
| RBC (x10 ¹² /L) | 4.23- 5.46 | 3.73-4.96 |
| Hb(g/L) | 130-168 | 114-150 |
| PCV (Ratio) | 0.390-0.500 | 0.350-0.450 |
| MCV (fl) | 83.5-99.5 | 83.5-99.5 |
| MCH (pg) | 27.5-33.1 | 27.5-33.1 |
| MCHC (g/L) | 315-350 | 315-350 |
| RDW | 10.0-16.0 | 10.0-15.9 |
| PLATELETS x(10 ⁹ /L) | 130-370 | 135-400 |
| NEUTS (x10 ⁹ /L) | 2.0-7.1 | 2.0-7.1 |
| LYMPHS (x10 ⁹ /L) | 1.1-3.6 | 1.1-3.6 |
| MONOs (x10 ⁹ /L) | 0.3-0.9 | 0.3-0.9 |
| EOSINS (x10 ⁹ /L) | 0.0-0.5 | 0.0-0.5 |
| BASOs (x10 ⁹ /L) | 0.0-0.2 | 0.0-0.2 |
| RETIC# | 20.0-92.0 | 12.0-96.0 |
| ESR ((mm/hr) | 1-10 | 1-20 |
 - Renal function:

| | | |
|------------------------------------|--------|--------|
| Creatinine (umol/L) | 60-125 | 55-110 |
| eGFR >59 mL/min/1.73m ² | | |

EXCLUSION CRITERIA

- Weight change of ≥ 3 kg in the preceding 2 months
- Undergone any weight loss surgery or gastric procedures to promote weight loss
- Current smokers
- Substance abuse
- Excess alcohol intake
- Pregnancy
- Diabetes
- Cardiovascular disease
- Cancer
- Gastrointestinal disease e.g. inflammatory bowel disease or irritable bowel syndrome
- Kidney disease
- Liver disease
- Pancreatitis
- Use of medications likely to interfere with energy metabolism, appetite regulation and hormonal balance, including: anti-inflammatory drugs or steroids, antibiotics, androgens, phenytoin, erythromycin or thyroid hormones.

Any participants with the above conditions would already have an altered pattern of hormones and inflammatory molecules because of their disease process and would therefore give us confounding or misleading results.

WITHDRAWAL CRITERIA

The safety of the study participants takes priority. Any significant adverse event (as assessed by the researchers) will halt the study and the ethics committee and sponsor will be informed as per standard protocol. All adverse events will be recorded and investigators will review each adverse event as it arises. In addition, participants will be free to withdraw at any time and are not required to give a reason.

STATISTICAL PLAN

Statistical analysis perform with IBM SPSS version 23. Graphs prepare with GraphPad Prism version 7.04. Data will be checked for normality using a Shapiro-Wilk test (defined as $P \geq 0.01$). Percentage of weight loss will be calculated using the weight at the end of the intervention divided by the baseline weight multiplied by 100. The results express as mean difference with \pm SEM. Mean of data will be compared within and between groups using a paired t-test or Wilcoxon signed-rank test where applicable. Analysis of variance will assess the impact of two different interventions (IPE and Inulin) on participant blood parameters across the 12-week supplementation period (baseline and week 12), with the supplementation group used to determine between-subjects differences. A p-value ≤ 0.05 will consider significant.

References:

- Abete, I. et al., 2008. Effects of two energy-restricted diets differing in the carbohydrate/protein ratio on weight loss and oxidative changes of obese men. *International journal of food sciences and nutrition*, 60 Suppl 3(783016891), pp.1–13. Available at: <http://www.ncbi.nlm.nih.gov/pubmed/18654910>.
- Bouché, C. et al., 2002. Five-week, low-glycemic index diet decreases total fat mass and improves plasma lipid profile in moderately overweight nondiabetic men. *Diabetes Care*, 25(5), pp.822–828.
- Brown, A.J. et al., 2003. The orphan G protein-coupled receptors GPR41 and GPR43 are activated by propionate and other short chain carboxylic acids. *Journal of Biological Chemistry*, 278(13), pp.11312–11319.
- Chambers, E.S. et al., 2015. A novel dietary strategy to increase colonic propionate production in humans and improve appetite regulation and bodyweight management. *Nutrition Bulletin*, 40(3), pp.227–230. Available at: <http://doi.wiley.com/10.1111/nbu.12157>.
- Chambers, E.S. et al., 2014. Effects of targeted delivery of propionate to the human colon on appetite regulation, body weight maintenance and adiposity in overweight adults. *Gut*, 64(11), pp.1744–1754. Available at: <http://www.ncbi.nlm.nih.gov/pubmed/25500202>.
- Cleave, T.L., 1974. The Saccharine Disease - Chapter 5. In Bristol. Available at: http://journeytoforever.org/farm_library/Cleave/cleave_ch5.html [Accessed February 28, 2016].
- Cordain, L. et al., 2005. Origins and evolution of the Western diet : health implications for the. *The American Journal of Clinical Nutrition*, 81, pp.341–354.

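### Does powering on diet alone versus diet plus IPE undermine the 80% power when the control arm takes diet plus inulin?

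*Combined protocol and SAP*

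**What the plan says.** The paragraph headed Support of number of volunteers gives the only justification of sample size. Its reference value is "Based on previous work we anticipate that a hypo-caloric diet alone will cause a weight loss of 3.0 ± 2.5 kg", set against 5.0 ± 2.5 kg when propionate ester is added. From these it derives 26 per group for a difference between groups at p=0.05 and power 0.80, and 70 recruits to cover 25% dropout.

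Under Visit 3 the randomised supplements are "10 g of Propionate ester or Inulin (control) dietary supplement once a day", and both are mixed into the individual −500 kcal/day diet. There is no diet-only arm. The Statistical Plan also names the two interventions: "Analysis of variance will assess the impact of two different interventions (IPE and Inulin". That sentence goes on to blood parameters. The comparison of weight rests on the plan's more general statement that means are compared within and between groups.

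The aim, at the end of the Introduction, names no comparator: "The current protocol aims to investigate the impact of the propionate ester in conjugation with restricted diet on appetite and weight loss".

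**The concern.** The 3.0 kg describes a condition that nobody in the trial receives. If inulin adds some weight loss of its own, the control mean lies above 3.0 kg, the contrast falls below 2.0 kg, and 26 per group no longer gives 80% power. At that size there is almost no margin, because the smallest difference with 80% power is 1.98 kg.

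The Introduction gives some reason to ask. On non-digestible carbohydrate (NDC) it says that "the addition of high fibre NDC foods to a hypocaloric diet would help reducing the incidence of metabolic syndrome and increasing the dietary compliance", and that "NDC ingestion was found to stimulate the release of these hormones in animals, resulting in decreasing food ingestion". Inulin belongs to that class. The protocol neither says that inulin is taken as inert nor gives an expected loss for diet plus inulin, and the source of the 3.0 kg is described only as previous work. At stake is how to read a null result: which difference the trial could detect, and against what.

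**Working it through.** **Inputs.** From Support of number of volunteers: means 3.0 and 5.0 kg, SD 2.5 kg in each arm, alpha 0.05, power 0.80, dropout 25%. Two assumptions are mine: a two-sided test and equal allocation. Neither is stated, but together they reproduce the published figure; a one-sided test would need only 20 to 21 per group.

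**Reproducing the plan's figure.**
- Difference: 5.0 − 3.0 = 2.0 kg. Standardised: 2.0 / 2.5 = 0.8.
- Normal approximation: n = 2(1.960 + 0.842)² / 0.8² = 24.5, so 25 per group.
- Two-sample t-test (noncentral t): n = 25.5, so 26 per group, as stated. Power at 26 is 80.7%.
- Dropout: 52 / (1 − 0.25) = 69.3, so 70, as stated.

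**What the 80% depends on.** The control mean enters the calculation only through the difference between arms. The figure therefore applies to IPE versus inulin if that difference is about 2.0 kg with SD 2.5 kg. The smallest difference with 80% power is 1.98 kg at 26 per arm and 1.70 kg at 35 per arm (all 70 analysed).

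**Sensitivity.** The differences other than 2.0 kg are assumed; the document supplies none of them. Two-sided t-test, SD 2.5 kg:

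| Difference, IPE − inulin | Power, 26 per arm | Power, 35 per arm |
|---|---|---|
| 2.0 kg | 81% | 91% |
| 1.75 kg | 70% | 82% |
| 1.5 kg | 56% | 70% |
| 1.0 kg | 29% | 38% |

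If inulin instead reduced the loss by 0.25 kg, the difference would be 2.25 kg and power at 26 per arm 89%.

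**How an inulin effect reaches the difference.** The Introduction (Short chain fatty acid ester) describes IPE as propionate esterified to an inulin carrier, so both arms take inulin. Suppose inulin adds e kg in the control arm, and a fraction f of this also adds to the IPE arm beyond the anticipated 5.0 kg. The difference is then 2.0 − e(1 − f). With e = 0.5 kg:
- f = 0 (the 5.0 kg already contains the carrier's effect): 1.5 kg, power 56%.
- f = 0.5: 1.75 kg, power 70%.
- f = 1: 2.0 kg, power 81%.

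The document gives neither e nor f.

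**What the document implies about e.** The two statements that make inulin look active concern high-fibre foods in a hypocaloric diet and food intake in animals. Neither is a weight result for a 10 g supplement. The same part of the Introduction then reads the propionate studies as "suggesting the owning of the beneficial effects of NDC on appetite and gut hormones to propionate production". It describes the colonic propionate reached with 10 g of IPE as "a level that is achieved only with 60g/d via traditional dietary fibre supplementation". By that reasoning 10 g of inulin should do much less than 10 g of IPE, though not provably nothing.

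**Precision of the result.** At 26 per arm and SD 2.5 kg, the standard error of the between-arm difference is 2.5 × √(2/26) = 0.69 kg. The 95% half-width is 2.01 × 0.69 = 1.39 kg, whatever the control mean was expected to be.

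**The case for a change.** The strongest case for a change is that the 2.0 kg may combine carrier and propionate. If the 5.0 kg for IPE includes any benefit of its inulin carrier while the 3.0 kg does not, the randomised contrast largely removes the carrier's share. The true target is then below 2.0 kg by an unknown amount. With the planned dropout the margin is about 0.02 kg, so even a small inulin effect matters. One sentence would settle it at no cost.

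Part of this stands. The label does not match the control arm, the no-effect assumption is unwritten, and f = 0 is a possible case. Three things limit it. First, no passage gives a weight effect for 10 g of inulin, so the argument shows how power could be lost, not that it is lost. The 60 g/d statement cannot supply a figure either: it gives no dose-response for propionate or for weight, and the same section says that fibre raises colonic short-chain fatty acids unpredictably. Second, the thin margin applies only if the full 25% drop out. With all 70 analysed, a 1.75 kg difference still has 82% power, so strict inertness of inulin is not required. Third, the added sentence would name a source or an assumption; the 26 per group, the 80% and the 2.0 kg would all remain.

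**Conclusion.** The mismatch in labelling is real but needs no change to the plan. The stated sample size is correct for a 2.0 kg difference with SD 2.5 kg. The paragraph itself speaks of a difference between groups, and the only groups are IPE and inulin. A statistician would read the 3.0 kg as the expected loss in a control arm thought to behave like diet alone, which fits the protocol's own account that propionate drives the effect.

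The comparator is open to any reader: the visit schedule labels inulin as the control, and the Statistical Plan names both interventions. A null result would therefore be read as IPE against inulin, and judged by the estimated difference and its precision (about ±1.4 kg at 26 per arm) more than by the planning value.

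This conclusion rests on a two-sided test, equal arms, SD 2.5 kg, and the absence of any documented weight effect of 10 g of inulin. If the previous work showed such an effect, power at 26 per arm could be well below 80% (56% at a 1.5 kg difference). The document gives no ground for assuming that. Whether or not the assumption is written down, the randomised comparison and its conclusion are equally sound.

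### Appetite ratings, buffet intake, breath hydrogen and energy expenditure get no baseline-adjusted comparison, although each is measured at Week 0 and again at Week 1 before supplementation

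*Combined protocol and SAP*

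**What the plan says.** The Introduction closes by giving the aim as to "investigate the impact of the propionate ester in conjugation with restricted diet on appetite and weight loss".

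Under Visit 2 (Week 0) the protocol states the purpose of the session: "The main objective of this visit is to fully acclimatize the participants to the study before the baseline visit". A full set of non-blood measurements is nevertheless taken there:

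- "Resting energy expenditure will be measured with a standard indirect calorimeter", which gives resting metabolic rate (RMR) and respiratory quotient (RQ).
- "Appetite and satiety will be assessed by visual analogue scale every 60 min and breath hydrogen concentration will be measured at the same time".
- "Food intake will be assessed at 240 min by offering a free buffet meal served in excess".

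Under Visit 3 (Week 1), "The same measurements collected during the acclimatization visit will be repeated", with blood taken in place of the saline flushes. Randomisation is first described under that visit. Visit 6 (Week 12) repeats the Week 1 measurements.

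The Statistical Plan names baseline and week 12 only for blood parameters, in an analysis of variance. For everything else it offers a paired t-test or a Wilcoxon signed-rank test, within and between groups. It names no appetite, buffet, breath hydrogen or calorimetry analysis, no baseline covariate for any outcome, and no role for Week 0.

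**The concern.** For these outcomes the plan leaves the between-arm comparison without baseline adjustment. Each participant has two earlier readings of the same quantity under nearly the same conditions. A reading taken before randomisation can enter the model as a covariate without biasing the comparison of arms. First-visit unfamiliarity, or a diet that starts between the two sessions, shifts both arms alike.

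What is at stake is precision, not validity. The only sample-size calculation is for weight loss, so nothing in the plan shows that 26 completers per group are enough for appetite. The silence also leaves open, until after the data are seen, which session counts as baseline and whether to adjust for it.

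**Working it through.** **The plan's own figure.** Support of number of volunteers gives losses of 3.0 and 5.0 kg, SD 2.5 kg, p = 0.05 and power 0.80. The standardised difference is 2.0/2.5 = 0.8. A two-sided two-sample t-test needs 25.5 per group, so 26, which agrees with the plan. With 25% drop-out, 52/0.75 = 69.3, so 70, which also agrees. This calculation concerns weight only, and nothing below changes it.

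**Inputs for this point.** There are three sessions (Weeks 0, 1 and 12) and 52 completers. The correlation r between sessions is not in the documents; I assume 0.3 to 0.8, with 0.5 to 0.7 as the central range. The plan does not say what is compared between arms, so I take change from Week 1 as the reference.

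**Formulas.** Variance of the arm contrast, relative to comparing Week 12 values alone, with the same r between any two sessions:

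- change from Week 1: 2(1 − r)
- ANCOVA on Week 1: 1 − r²
- ANCOVA on Week 1 and Week 0: 1 − 2r²/(1 + r)

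| r | Change | Week 1 only | Weeks 0 and 1 | Cut from Week 1 alone | Further cut from Week 0 |
|---|---|---|---|---|---|
| 0.3 | 1.40 | 0.910 | 0.862 | 35% | 5.3% |
| 0.5 | 1.00 | 0.750 | 0.667 | 25% | 11.1% |
| 0.6 | 0.80 | 0.640 | 0.550 | 20% | 14.1% |
| 0.7 | 0.60 | 0.510 | 0.424 | 15% | 17.0% |
| 0.8 | 0.40 | 0.360 | 0.289 | 10% | 19.8% |

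The fifth column is (1 − r)/2. The last column is relative to the variance left after Week 1 adjustment.

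**Cost of the extra covariate.** At 52 completers it inflates variance by about 48/47 = 1.021, or 2%. The net further gain from Week 0 is then 1 − 0.889 × 1.021 = 9% at r = 0.5 and 1 − 0.830 × 1.021 = 15% at r = 0.7.

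**Unequal correlations.** Write a for Weeks 0–1, b for Weeks 0–12 and c for Weeks 1–12. With two covariates, R² = (b² + c² − 2abc)/(1 − a²).

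- a = 0.7, b = 0.5, c = 0.5: R² = 0.15/0.51 = 0.294. Residual variance is 0.706 against 0.750, a 5.9% gain, or 3.9% net.
- a = 0.7, b = 0.4, c = 0.5: R² = 0.13/0.51 = 0.255. Residual variance is 0.745 against 0.750, a 0.7% gain, or a net loss of 1.5%.
- a = 0.7, b = 0.35, c = 0.5: R² = 0.1275/0.51 = 0.250. There is no gain, and a net loss of 2.1%.

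**Averaging instead of separate covariates.** Using the plain mean of the two sessions, the second pattern raises residual variance by 1.6% and the third by 5.0%. Separate covariates avoid that loss apart from the one degree of freedom.

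**The case against.** The strongest reply is that Week 0 is a practice session by design. Treating a first encounter with the canopy, the rating scales and the buffet as rehearsal is a defensible choice, and the sentence that says so contains no error. That stands as a reason not to make Week 0 the sole baseline. It does not bar Week 0 as a covariate, and it is no reason to leave Week 1 unused as one.

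The second reply concerns size, and it stands in full. Weeks 0 and 1 are about a week apart, while Week 12 follows 84 days of supplement and diet. At Week 0, "a -500 kcal/day diet will be provided to the participants to follow for the rest study period", and the documents leave unclear whether Week 1 is already on that diet. The two early sessions may therefore correlate more with each other than with Week 12, and Week 0 may be the weaker predictor. A shift shared by both arms answers the worry about bias but not this one about precision.

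The third reply is that the larger gap is the absence of any named appetite analysis, and that hourly ratings and breath hydrogen have no defined session summary. Both are true, and the fix has to supply them.

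Two stronger readings are tempting. A reader might infer that ignoring Week 0 costs the whole 29% to 33% by which two-baseline ANCOVA beats a change score at r = 0.7 to 0.5 (1 − 0.424/0.60 and 1 − 0.667/1.00). Of that, 15 to 25 points come from adjusting for Week 1 alone. A reader might also infer that the plan discards Week 0. It is silent rather than exclusionary, and Visit 2 places the calorimetry and the energy estimate for the individual diet in the same session.

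**Conclusion.** The point holds as a minor, optional improvement. The plan provides no baseline-adjusted comparison for appetite ratings, buffet intake, breath hydrogen, RMR or RQ, although two earlier readings of each are already scheduled.

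The more secure part is adjustment for Week 1, worth 25% to 15% of variance against a change score at r of 0.5 to 0.7. The Week 0 part is a likely but not guaranteed modest gain: 11% to 17% of the remaining variance under equal correlations, about 5% at r = 0.3, and about zero or a small net loss if Week 0 predicts Week 12 less well than Week 1 does.

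These sizes rest on assumed correlations and on change from Week 1 as the comparator. They also assume that the Week 1 measurements are complete before allocation takes effect; the protocol implies this by treating Week 1 as baseline but does not set out the order within the day. Nothing here threatens validity or the sample size for weight loss.

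**What to change.** Add to the Statistical Plan: For appetite ratings, breath hydrogen, buffet intake, RMR and RQ, the Week 12 value will be compared between arms by ANCOVA, with the Week 1 value as a covariate and the Week 0 value as a second, separate covariate. Hourly measures will first be reduced to one session summary, named here and computed identically at all three sessions. Missing Week 0 values will be filled with the overall mean across both arms.

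The sponsor must choose the session summary before any comparison by arm. The two early sessions should not be averaged.

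The cost is wording only, with no new visit, sample or participant burden. The Week 0 covariate uses one degree of freedom, about 2% of variance at 52 completers.
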